6.2.2.3 Dose modification for renal impairment

No specific dose adjustment is needed in patients with mild or moderate renal impairment.

In patients with severe renal impairment (creatinine clearance less than 30 mL/min) the recommended starting dose based on platelet count should be reduced by approximately 50% BID (15mg BID or 25mg BID should have the higher dosage taken in the morning). Patients diagnosed with severe renal impairment while receiving ruxolitinib should be carefully monitored and need to have their doses reduced to avoid adverse drug reactions.

There are limited data to determine the best dosing options for patients with end-stage renal disease on hemodialysis. Available data in this population suggest that the starting dose for patients with end-stage renal disease on hemodialysis is 15 mg INC424 for patients with platelet count between 100,000-200,000/µL or 20 mg for patients with platelet count of >200,000/µL. Subsequent doses (single administration) should be administered on hemodialysis days following each dialysis session. Additional dose modification should be made with careful monitoring of safety and efficacy. No data is available for dosing patients who are undergoing peritoneal dialysis or continuous venovenous hemofiltration. No data is available for patients who have lower platelet counts and renal failure.

6.2.2.4 Dose modification for hepatic impairment

Patients diagnosed with hepatic impairment while receiving ruxolitinib should be carefully monitored and may need to have their dose reduced to avoid adverse drug reactions.

In patients with any hepatic impairment the recommended starting dose based on platelet count should be reduced by approximately 50% BID (15mg BID or 25mg BID should have the higher dosage taken in the morning). Subsequent doses should be adjusted based on careful monitoring of safety and efficacy. Patients diagnosed with hepatic impairment while receiving INC424 should have complete blood counts, including a white blood cell count differential (neutrophils, lymphocytes, eosinophils, basophils, monocytes, and blast cells), monitored at least every one to two weeks for the first 6 weeks after initiation of therapy with INC424 and as clinically indicated thereafter once their liver function and blood counts have been stabilized. INC424 dose can be titrated to reduce the risk of cytopenia.

[REDACTED]

6.2.3 Restarting or reinstating previous dose

6.2.3.1 Restarting or reinstating previous dose for patients who start INC424 15 – 20 mg BID

Dosing of INC424 may be restarted or increased following recovery of platelet counts and/or ANC to acceptable levels as illustrated in [Table 6-4](#) for those patients who start on INC424 15 – 20 mg BID. The objective for restarting or escalating after a reduction for safety is to find the highest safe dose of INC424 for each patient, with increases in dose generally not more than in increments of 5 mg BID and not more often than every 2 weeks. Patients who are restarting after a reduction for thrombocytopenia may not receive doses above 20 mg BID maximum. Similarly, ANC levels that decline to < 500/ μ L necessitate immediate dose interruption ([Section 6.2.6](#)). ANC level recovery to 500 / μ L and above but less than 750/ μ L will allow dosing to be restarted at 5 mg BID, and ANC levels between 750/ μ L, but < 1000/ μ L may restart at 10 mg BID. Absolute neutrophil count level increases to above 1000/ μ L will allow a further dose increase to a maximum of 20mg BID.

The maximum dose used should never exceed 5mg BID LESS than any dose that resulted in platelets falling below 100,000/ μ L or ANC falling below 500/ μ L. After restarting using the guidelines in [Table 6-4](#), if it is found that a patient cannot tolerate the lowest allowed dose (5mg BID, or 5mg QD with concomitant CYP3A4 inhibitor, see [Section 6.2.4](#)) without platelets falling below 50,000/ μ L, neutrophils falling below 500/ μ L, or Hgb falling below 6.5g/dL despite the use of transfusion therapy, drug must be permanently discontinued ([Section 6.2.6](#), and [Section 7.6.1](#)).

Table 6-4 **Restarting or increasing INC424 dose after safety interruptions or dose reductions for patients starting on doses of 15 – 20 mg BID**

Current Platelet Count	Dose Restart or Dose Increase Guidelines
< 50,000/ μ L	Continue hold
50,000/ μ L to < 75,000/ μ L	5 mg BID for at least 2 weeks; if stable, may increase to 10 mg BID
75,000/ μ L to < 100,000/ μ L	10 mg BID for at least 2 weeks; if stable, may increase to 15 mg BID
100,000/ μ L to < 125,000/ μ L	15 mg BID
\geq 125,000/ μ L	20 mg BID
Current ANC Level	Dose Restart or Dose Increase Guidelines
< 500/ μ L	Continue hold
500 to < 750/ μ L	5 mg BID for at least 2 weeks; if stable, may increase to 10 mg BID
750 to < 1000/ μ L	10 mg BID for at least 2 weeks; if stable, may increase to 15 mg BID
1000 to < 1500/ μ L	15 mg BID for at least 2 weeks; if stable may increase to 20 mg BID
\geq 1500/ μ L	20 mg BID

NOTE: Whether the dose interruption occurred because of neutropenia, thrombocytopenia or both, when restarting, both the platelet count and ANC must be considered to determine the restart dose, with the lower calculated dose being used.

6.2.3.2 Restarting or reinstituting previous dose for patients who start INC424 at 5 mg BID

Dosing of INC424 may be restarted or increased following recovery of the platelet count to $\geq 50,000/\mu\text{L}$. Reinitiate treatment at a dose of 5 mg o.d. The dose may be increased by 5 mg o.d. every two weeks based on platelet counts and the absence of other adverse events.

When the ANC is $< 500/\mu\text{L}$, hold INC424 dosing. INC424 can be reinitiated in this population once the ANC is $\geq 500/\mu\text{L}$, at a dose of 5 mg o.d. The dose may be increased by 5 mg o.d. every two weeks based on platelet counts and the absence of other adverse events.

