6.2.2 Dose interruption or dose reduction

For patients who do not tolerate the protocol-specified dosing schedule, dose adjustments are permitted in order to allow the patient to continue the study treatment. The following guidelines need to be applied: for all patients who are receiving INC424, there are mandatory dose decreases or dose interruptions for declining platelet counts or ANC levels that might be observed while on INC424 therapy. In addition to mandatory dose interruption or decrease for hematologic toxicities, there are mandatory criteria for permanent discontinuation of INC424 (See [Section 6.2.6](#)).

Dosing must be held if platelet counts decline below 50,000/ μ L (Grade 3 laboratory abnormality by CTCAE v. 3.0, or if ANC falls below 500/ μ L while receiving INC424.

6.2.2.1 Dose interruption or dose reduction for patients starting INC424 at doses of 15 – 20 mg p.o. BID

Doses should be decreased for platelet count values < 125,000/ μ L as shown in [Table 6-2](#) with optional restarting or resuming prior dose after recovery ([Section 6.2.3](#)). In order to provide sufficient data to make the dose adjustment decisions, it is recommended that hematology parameters be obtained at least weekly for platelet count <100,000/ μ L or ANC < 1000/ μ L and at least two times weekly for platelet count < 50,000/ μ L or ANC < 500/ μ L.

These changes must be recorded on the Dosage Administration Record eCRF.

Table 6-2 Dose reductions in INC424 for safety in patients with platelet count declines (for those starting on INC424 dose of 15 – 20 mg p.o. BID)

[figure not shown]
Platelet Count at Time of Decline	Dose at the Time of Platelet Decline				
	25 mg BID	20 mg BID	15 mg BID	10 mg BID	5 mg BID
Dose that MUST be Instituted					
≥ 125,000/ μ L	No dose reduction required				
100,000/ μ L to < 125,000/ μ L	20 mg BID	20 mg BID	15 mg BID	10 mg BID	5 mg BID
75,000/ μ L to < 100,000/ μ L	10 mg BID	10 mg BID	10 mg BID	10 mg BID	5 mg BID
50,000/ μ L to < 75,000/ μ L	5 mg BID	5 mg BID	5 mg BID	5 mg BID	5 mg BID
< 50,000/ μ L	Stop Dosing				

6.2.2.2 Dose interruption or dose reduction for patients starting INC424 at doses of 5 mg p.o. BID

Dose modifications are made according to the platelet count as follows (see [Table 6-3](#)):

- If platelets > 25,000 - < 50,000/ μ L: reduce the INC424 dose by 5 mg o.d.
- If platelets ≤ 25,000/ μ L: hold treatment. Treatment can be restarted at a later date if platelets increase to ≥ 50,000/ μ L.

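### For patients starting on 15–20 mg BID, Table 6-4 lists restart doses above the Section 6.2.3.1 cap, and the table's NOTE leaves the cap out

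*Protocol*

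**What the plan says.** All of this concerns patients who start on 15 or 20 mg BID.

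- **Cap (Section 6.2.3.1, text above Table 6-4).** "The maximum dose used should never exceed 5mg BID LESS than any dose that resulted in platelets falling below" 100,000/µL, or ANC below 500/µL. It depends on the dose the patient was taking when the count fell.
- **Table 6-4.** It gives a dose for each band of current platelet count and current ANC. The platelet row for 75,000 to <100,000/µL reads "10 mg BID for at least 2 weeks; if stable, may increase to 15 mg BID"; the ANC row for 750 to <1000/µL uses the same words. The ANC row for 1000 to <1500/µL reads "15 mg BID for at least 2 weeks; if stable may increase to 20 mg BID". The top row of each block is 20 mg BID.
- **NOTE under Table 6-4.** On restarting, "both the platelet count and ANC must be considered to determine the restart dose, with the lower calculated dose being used". The cap is not mentioned.
- **Section 6.2.2.1 and the synopsis (Dose, regimen, treatment).** Both describe reductions "with optional restarting or resuming prior dose after recovery" and point to Section 6.2.3.
- **Lowest dose.** The sentence after the cap requires permanent discontinuation if "a patient cannot tolerate the lowest allowed dose (5mg BID, or 5mg QD with concomitant CYP3A4 inhibitor") without a further severe fall in counts or hemoglobin. Table 6-2 keeps a patient already on 5 mg BID at 5 mg BID while platelets are 50,000 to <100,000/µL.

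**The concern.** One rule looks back at the dose that preceded the fall. The other looks only at today's counts. The NOTE reads as the complete recipe for choosing a restart dose, and it takes the lower of two doses when the section contains three limits. A site working from the table and NOTE could return a patient to the dose on which the count fell, or go above it: a fall on 15 mg BID, then 20 mg BID once platelets reach 125,000/µL. A site working from the paragraph above the table would stop at 10 mg BID for the same patient.

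The protocol describes thrombocytopenia as the dose-limiting toxicity of this drug, so what is at stake is repeat cytopenia and different dosing between sites.

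**Working it through.** The plan gives no figure to reproduce. The check compares the two rules cell by cell.

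**Inputs.** The cap is from Section 6.2.3.1, the restart doses from Table 6-4, and the mandatory reductions from Table 6-2.

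**Formula.** Cap = dose at the time of the fall − 5 mg BID. A fall on 20 gives 20 − 5 = 15. A fall on 15 gives 15 − 5 = 10. A fall on 25 gives 20, which the table never exceeds, so that case raises no conflict.

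**Comparison for the two starting doses (mg BID).** Brackets show the optional increase after two weeks. Each row assumes that the other count is not the limiting one.

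| Current count (/µL) | Table 6-4 dose | Fall on 20, cap 15 | Fall on 15, cap 10 |
|---|---|---|---|
| Platelets 50,000 to <75,000 | 5 (10) | within | within |
| Platelets 75,000 to <100,000 | 10 (15) | within | above only after increase, +5 |
| Platelets 100,000 to <125,000 | 15 | within | above, +5 |
| Platelets ≥125,000 | 20 | above, +5 | above, +10 |
| ANC 500 to <750 | 5 (10) | within | within |
| ANC 750 to <1000 | 10 (15) | within | above only after increase, +5 |
| ANC 1000 to <1500 | 15 (20) | above only after increase, +5 | above, +5 (+10 after increase) |
| ANC ≥1500 | 20 | above, +5 | above, +10 |

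**Counts.**
- Listed dose above the cap: platelets 1 + 2 = 3 of 8; ANC 1 + 2 = 3 of 8; together 6 of 16.
- With optional increases: platelets 1 + 3 = 4 of 8; ANC 2 + 3 = 5 of 8; together 9 of 16.

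**How often the cap is in force after a platelet-triggered change.** In Table 6-2, a patient on 20 or 15 mg BID needs no change at 100,000/µL or above. Required changes are 20→10 and 15→10 at 75,000 to <100,000; 20→5 and 15→5 at 50,000 to <75,000; and a stop for both below 50,000. That is 2 + 2 + 2 = 6 cells, all below 100,000/µL. The cap therefore applies after every platelet-triggered change from these doses. The prior dose is then always 5 mg BID above the cap, so the offer to resume it is always barred.

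**Lower end.** After a platelet fall to 50,000 to <100,000/µL on 5 mg BID, the literal cap is 5 − 5 = 0 mg, while Table 6-2 keeps the patient on 5 mg BID.

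**The case against.** The best defence is that nothing is really in conflict. The cap is worded as an absolute maximum, the table column is headed as guidelines, and its increases are permissive. A firm ceiling and a permissive table in one subsection are ordinarily read as the lower of the two, and the cap stands directly above the table. That is the natural reading, and a site that follows it doses within the cap. It does not remove the problem, because the NOTE states how the restart dose is determined and omits the cap, and the prior-dose offer runs against it.

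Other safeguards help only in part. The same section generally limits increases to 5 mg BID steps at least two weeks apart, which slows the climb but does not lower its end point. The recommended weekly or twice-weekly counts detect a repeat fall but do not prevent it. Sponsor approval under Section 6.2.6 covers restarts after a temporary stop for an adverse experience, not re-escalation after a reduction.

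Some stronger readings are tempting but unsupported:

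- **Two competing restart doses.** The cap is a ceiling, not a second restart dose.
- **The two 20 mg BID limits contradict the cap.** The sentences "Patients who are restarting after a reduction for thrombocytopenia may not receive doses above 20 mg BID maximum" and, for ANC above 1000/µL, "will allow a further dose increase to a maximum of 20mg BID" are upper bounds, and several upper bounds can hold together. The first also does separate work after a 25→20 reduction at 100,000 to <125,000/µL, where the cap is not triggered.
- **The zero cap after ANC <500/µL on 5 mg BID.** That case is largely covered by the permanent-discontinuation rule in Sections 6.2.3.1 and 6.2.6. The platelet case at 50,000 to <100,000/µL is not.
- **A patient count.** The figure of 36.9% in Section 1.3.5 for thrombocytopenia leading to reduction or interruption comes from the Phase III trials and does not count restarts.

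The Amendment 2 summary describes removing a platelet limit of this kind. A change log is not evidence of an error in the current text, and nothing here rests on it.

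**Conclusion.** The point holds as an unreconciled dosing rule that should be corrected. For falls on the two starting doses, Table 6-4 lists a dose above the cap in 6 of 16 combinations, or 9 of 16 with optional increases, by 5–10 mg BID. The prior-dose offer conflicts with the cap after every platelet-triggered change from 15 or 20 mg BID. The cap also lacks a stated floor for platelet falls on 5 mg BID.

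The counts are table cells, not patients; the documents give no basis for a restart rate in this study. They assume that the cap is meant to apply to restart and re-escalation, and that platelet and ANC rows are considered one at a time. Conflict between sites arises only where the table and NOTE are used without the paragraph above them. No analysis set, endpoint, sample size or statistical result depends on this.

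**What to change.** 1. Add a footnote to Table 6-4 that refers to the cap, and reword the NOTE along these lines: *Use the lowest of the platelet-based dose, the ANC-based dose and the Section 6.2.3.1 cap. The cap does not go below 5 mg BID (5 mg QD with a CYP3A4 inhibitor), and the permanent-discontinuation rules still apply.*
2. Add *subject to the Section 6.2.3.1 cap* to the prior-dose offer in Section 6.2.2.1 and in the synopsis.
3. If the sponsor does not intend the platelet cap, remove only the platelet clause. Keep the ANC <500/µL cap with the same footnote; deleting the whole sentence would drop that protection too.

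The text change is one footnote, one reworded NOTE and a few words in two places. It needs a written amendment with the approvals in Section 12.11, so it is best joined to the next planned amendment. Enrollment ended on 31 December 2014, so the benefit is for patients still on treatment, with the last visit expected in December 2016.

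### For patients starting at 15–20 mg BID, Table 6-4 permits step-up doses that Table 6-2 says must be cut in the same platelet bands, and nothing says which table governs

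*Protocol*

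**What the plan says.** Both tables are titled for patients whose starting dose was 15–20 mg BID.

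- **Protocol Table 6-4** (Section 6.2.3.1) covers restarting or raising the dose after a safety interruption or reduction. Its 50,000 to <75,000/µL row reads "5 mg BID for at least 2 weeks; if stable, may increase to 10 mg BID". Its 75,000 to <100,000/µL row reads "10 mg BID for at least 2 weeks; if stable, may increase to 15 mg BID". The section introduces these as permissions: "Dosing of INC424 may be restarted or increased following recovery of platelet counts and/or ANC to acceptable levels".
- **Protocol Table 6-2** (Section 6.2.2.1) is set out under "Dose that MUST be Instituted". At 50,000 to <75,000/µL every listed dose becomes 5 mg BID. At 75,000 to <100,000/µL, doses of 10 mg BID and above become 10 mg BID.
- **The Table 6-2 trigger** is worded in two ways. The row heading is "Platelet Count at Time of Decline", and Section 6.2.2 speaks of "mandatory dose decreases or dose interruptions for declining platelet counts or ANC levels". Section 6.2.2.1 instead says "Doses should be decreased for platelet count values < 125,000"/µL. The synopsis repeats that count-value wording under a statement that reduction or interruption is mandatory for these starters.
- **A cap** in Section 6.2.3.1 limits re-escalation: "The maximum dose used should never exceed 5mg BID LESS than any dose that resulted in platelets falling below 100,000"/µL.

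**The concern.** The optional table allows a dose that the mandatory table does not allow at the same count for the same patients. Nothing ranks the two after a Table 6-4 increase. The nearest text, at the end of Section 6.2.1.1.2, says that the safety adjustments and the restart rules apply to the original dose and to a dose raised for lack of efficacy. A dose raised under Table 6-4 is not mentioned.

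Two things are at stake. Sites that each follow the protocol can give the same thrombocytopenic patient different doses. And reductions produced by the rules, with no material change in the patient's count, enter the exposure and safety output.

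**Working it through.** There is no stated figure to reproduce. The check sets the tables side by side and then applies the cap. ANC is assumed not to limit the dose.

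**1. Cell by cell.** Each Table 6-4 dose is looked up in the Table 6-2 cell for the same platelet band.

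| Band (/µL) | Table 6-4 dose (mg BID) | Table 6-2 dose for a patient on it (mg BID) | Result |
|---|---|---|---|
| 50,000 to <75,000 | restart 5 | 5 | agree |
| 50,000 to <75,000 | step-up 10 | 5 | conflict, 10/5 = 2-fold |
| 75,000 to <100,000 | restart 10 | 10 | agree |
| 75,000 to <100,000 | step-up 15 | 10 | conflict, 15/10 = 1.5-fold |
| 100,000 to <125,000 | 15 | 15 | agree |
| ≥125,000 | 20 | no reduction | agree |

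Below 50,000/µL both tables withhold drug. So two of the four dosing rows conflict, and only at the step-up dose.

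**2. The cap.** Maximum dose = dose on which platelets fell below 100,000/µL, minus 5 mg BID.

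| Fall occurred on (mg BID) | Cap (mg BID) | Step to 15 at 75,000 to <100,000 | Step to 10 at 50,000 to <75,000 |
|---|---|---|---|
| 25 | 20 | open | open |
| 20 | 15 | open | open |
| 15 | 10 | blocked | open |
| 10 | 5 | blocked | blocked |

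**3. The trigger.** Suppose every optional increase is taken and the count stays constant, in 2-week steps.

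- *Count-value reading, cut does not lower the cap.* At 60,000/µL after a fall on 15 or 20 mg BID, the dose runs 5, 10, 5, 10. At 85,000/µL after a fall on 20 mg BID, it runs 10, 15, 10, 15.
- *Count-value reading, stepped-up dose counts as one that caused a fall.* The cap drops and there is one up-and-down: 5, 10, 5 and then 5 throughout, or 10, 15, 10 and then 10 throughout.
- *Decline reading.* A constant count gives no cut. No size of fall or reference point is given, however. If the reference is the previous draw, 60,000 followed by 58,000 is enough. If it is baseline, any count in these bands qualifies, because Section 6.1.1 gives 15–20 mg BID starts only to patients at 100,000/µL or above.

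**4. Where it shows in the analysis.** SAP Section 3.2 counts any move to a smaller total daily dose as a reduction. Protocol Section 11.4 summarises reductions by reason. SAP Section 3.5.1 summarises AEs leading to dose adjustment. Under Protocol Section 9.1.1, a laboratory abnormality that requires a change in study medication is itself an AE. The primary variable (Protocol Section 11.5.1, SAP Section 3.4.1.1) counts a patient once per preferred term.

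**The case against.** The best defence is that the tables serve different situations: Table 6-2 when counts are falling, Table 6-4 when they have recovered. Different doses at one count are then by design. The count-value sentence in Section 6.2.2.1 itself goes on to point to Table 6-2 and to optional resumption after recovery under Section 6.2.3. A mandatory rule would also naturally override an optional one, and Table 6-4 offers guidelines with a permissive step-up.

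Part of this stands. On the decline reading a patient with a truly constant count is not cut. A reader might infer that a stable patient will be cycled up and down indefinitely. That needs the count-value trigger, a cap that the stepped-up dose does not lower, and an investigator who takes each optional increase; the documents do not establish all three. Nor can one say that the conflict arises at once through weekly draws, because Section 6.2.2.1 only recommends weekly hematology below 100,000/µL.

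The defence does not settle the matter. Section 6.2.2 applies the mandatory decreases to every patient on drug and does not exempt those stepped up. Table 6-2 has columns for 10 and 5 mg BID, which 15–20 mg BID starters mostly reach through a safety reduction or restart, so it appears to include the Table 6-4 population. Neither *decline* nor *stable* is defined, and no sentence states that the mandatory table overrides the optional one.

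**Conclusion.** The conflict is real and limited to the step-up doses: 10 against 5 mg BID at 50,000 to <75,000/µL, and 15 against 10 mg BID at 75,000 to <100,000/µL. A patient may be stepped up and then cut at essentially the same count: at any draw on the count-value reading, or after any small fall on the decline reading if the previous draw is the reference. The cap leaves both steps open after a fall on 20 or 25 mg BID, one after a fall on 15 mg BID and none after a fall on 10 mg BID. It may also hold the pattern to one up-and-down.

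Two larger claims are not supported. First, a reader might infer distortion of the primary endpoint. Patients reach Table 6-4 only after an interruption or reduction, and incidence counts each patient once per preferred term, so that effect is small; the dose-reduction and dose-adjustment summaries carry most of it. Second, a reader might apply the 36.9% Phase III rate of dose reduction or interruption for thrombocytopenia (Protocol Section 1.3.5) to the 2238 enrolled: 2238 × 0.369 ≈ 826, or about 661 if 80% started at 15–20 mg BID, a share the documents do not give. That would count any thrombocytopenia-driven adjustment, not patients in these bands who were stable, stepped up, not capped and then triggered. The documents give no rate for that group.

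**What to change.** Reconcile Tables 6-2 and 6-4, the trigger wordings in Sections 6.2.2 and 6.2.2.1 and in the synopsis, and the cap in Section 6.2.3.1. State which rule applies to a patient already raised under Table 6-4, what counts as a decline (size and reference point) and as stable, and whether a stepped-up dose that is later cut lowers the cap. The sponsor's clinical team decides which rule governs; no dose is proposed here.

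The cost is amendment wording and a site letter, with no added procedures or patients. Recruitment ended on 31 December 2014, but the last patient visit is expected in December 2016, so a clarification can still reach patients on treatment under the current protocol.

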	
following conditions are met:
 
- Palpable spleen length below the costal margin that has been reduced by < 40% at the Week 4 visit relative to baseline.- Platelet count at the Week 4 blood draw is > 150,000/μL and platelet count has never been < 150,000/μL at a prior laboratory assessment while receiving INC424 (Figure 6-1).- ANC levels have remained \geq1000/μL since enrollment in the study. 
Additional dose increases beyond the week 4 dose escalation for patients who start on 15 – 20 mg BID of INC424 are permitted, at the discretion of the investigator, as follows:
 
- The patient must not have had a prior safety-related dose reduction.- The patient must have had a platelet count \geq 150,000/μL at every assessment since baseline.- The patient must have had ANC \geq 1000/μL at every assessment since baseline.- The dose increase may only be an increase of 5 mg BID.- The total dose may never exceed 25 mg BID. 
For those patients who start INC424 treatment at a dose of 5 mg BID, dose increases can be made, at the discretion of the investigator, as described below. The dose can be escalated 5 mg once a day starting at week 4, and thereafter no more than every two weeks ONLY if:
 
- The patient must not have had a prior safety-related dose reduction.- Platelet count remains \geq 50,000/μL since last lab scheduled visit.- ANC $>$ 1000/μL since last scheduled visit.- No dose reduction or interruption for safety occurred in the preceding weeks after the last planned visit.- The dose increase may only be an increase of 5 mg o.d. i.e., from 5 mg PO BID to 5 mg QAM and 10 mg QPM.- The total dose may never exceed 25 mg BID. 
Following a dose increase, platelet count and ANC levels should be assessed approximately 2 weeks after the dose adjustment. If a regularly scheduled Study Visit does not coincide with this required blood draw, an unscheduled Interim Visit should be held to collect samples for hematology.
 
Dose interruption or dose reduction (Section 6.2.2) is mandatory as follows for patients who start on dose of 15 – 20 mg BID:
 
Dosing must be held if platelet counts decline to < 50,000/μL (Grade 3 laboratory abnormality by CTCAE v. 3.0, or if ANC falls below 500/μL while receiving INC424.
 
Doses should be decreased for platelet count values < 125,000/μL as shown in Table 6-2 with optional restarting or resuming prior dose after recovery Section 6.2.3 In order to provide sufficient data to make dose adjustment decisions, it is recommended that hematology parameters be obtained at least weekly for platelet count <100,000/μL or ANC < 1000/μL and at least two times weekly for platelet count < 50,000/μL or ANC <500/μL.
 
Dose interruptions or dose reductions for patients starting INC424 5 mg BID: dose

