Dose adjustments for safety (Section 6.2.2), and reinstatement of doses (Section 6.2.3) will apply whether the patient is on the original dose, or a dose that was increased for lack of efficacy.

6.2.1.2 Dose modification for patients starting INC424 at a dose of 5 mg BID

6.2.1.2.1 Dose increases at week 4

For those patients who start INC424 treatment at a dose of 5 mg BID, dose increases can be made as described below. The dose can be escalated 5 mg once a day starting at week 4, and thereafter no more than every two weeks ONLY if:

- Inadequate efficacy is seen with the current dose level (See [Section 6.2.1.1.1](#))
- No treatment-related toxicity has occurred with the current dose level, resulting in treatment reduction or interruption or discontinuation in the previous 28 days
- The minimum platelet count at the time of the escalation is $\geq 50,000/\mu\text{L}$
- ANC $> 1000/\mu\text{L}$ since last scheduled visit
- The total dose may never exceed 25 mg BID

[figure not shown]
If the above criteria are met, then the INC424 dose can be increased by 5 mg o.d. e.g., from 5 mg BID to 5 mg QAM and 10 mg QPM.

6.2.1.2.2 Dose increases beyond week 4

After Week 4, dose increases of INC424 are allowed for those patients who exhibit an INCREASE in palpable spleen length. The rules for these optional dose increases are as follows:

- The dose increases may only occur if the platelet count and ANC data for that visit are available.
- The palpable spleen length for that Study Visit must show a 2 cm or greater INCREASE in length compared to the on-study nadir (lowest palpable spleen measurement during the study, including Baseline).
- The patient must NOT have had a prior safety-related dose reduction.
- The following platelet threshold have been met:
 - The patient must have had a platelet count $\geq 50,000/\mu\text{L}$ at every assessment since Baseline for those starting INC424 at a starting dose of 5 mg BID
- The patient must have had ANC $\geq 1000/\mu\text{L}$ at every assessment since baseline.
- The dose increase may only be an increase of 5 mg once daily for those starting on an INC424 dose of 5 mg BID.
- The total dose may never exceed 25 mg BID.
- Following a dose increase, platelet count and ANC levels should be assessed approximately 2 weeks after the dose adjustment. If a regularly scheduled Study Visit does not coincide with this required blood draw, an unscheduled Interim Visit should be held to collect samples for hematology.

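### For 5 mg BID starters, Protocol 6.2.3.2 allows stepwise increases after a safety hold or reduction without saying where they end, while the synopsis and 6.2.1.2.2 bar increases after a safety reduction, and no passage says which governs

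*Protocol*

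**What the plan says.** Protocol 6.2.3.2 covers restarting or reinstituting the previous dose in patients who start at 5 mg BID. Its opening sentence lets dosing be restarted or increased once platelets recover to at least 50,000/µL. After a hold the instruction is "Reinitiate treatment at a dose of 5 mg o.d", and then "The dose may be increased by 5 mg o.d. every two weeks based on platelet counts and the absence of other adverse events". The same restart dose and step apply after a neutrophil hold, once ANC is at least 500/µL.

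Three other places set conditions on increases in the same patients:

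- The synopsis (Dose, regimen, treatment) allows increases only under a list of conditions. They include "The patient must not have had a prior safety-related dose reduction" and "No dose reduction or interruption for safety occurred in the preceding weeks after the last planned visit".
- Section 6.2.1.2.1 (increases at week 4) requires: "No treatment-related toxicity has occurred with the current dose level, resulting in treatment reduction or interruption or discontinuation in the previous 28 days".
- Section 6.2.1.2.2 (increases beyond week 4) requires: "The patient must NOT have had a prior safety-related dose reduction". It also requires platelets of at least 50,000/µL "at every assessment since Baseline for those starting INC424 at a starting dose of 5 mg BID", and ANC of at least 1000/µL at every assessment since baseline.

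For patients who start at 15–20 mg BID, 6.2.3.1 states limits on re-escalation. One is absolute: "Patients who are restarting after a reduction for thrombocytopenia may not receive doses above 20 mg BID maximum". The other holds the dose at least 5 mg BID below any dose at which platelets fell under 100,000/µL or ANC under 500/µL.

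**The concern.** A 5 mg BID starter who has had a safety hold or reduction meets two sets of current instructions. One permits increases at two-week intervals; the other bars them. No passage says where reinstatement ends and an ordinary dose increase begins, or which rule prevails when both could apply. Section 6.2.1.2 closes by saying that 6.2.3 applies to original and increased doses alike, which does not settle precedence.

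This group enters with platelets of 50,000 to under 100,000/µL. The protocol plans a safety interim analysis for it (11.7) and displays it separately (section 11, statistical reporting and grouping). If sites read the rules differently, exposure after a cytopenia, and possibly later cytopenia counts in this group, will partly reflect the section each site followed.

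**Working it through.** No sample-size, power or error-rate figure bears on this point, and the plan states none to reproduce. The check compares the rules and counts dose steps.

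**Rules for 5 mg BID starters**

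| Place | Increase after a safety reduction | Increase after a safety hold | Stated end |
|---|---|---|---|
| 6.2.3.2 | Allowed on recovery | Allowed on recovery, +5 mg o.d. every two weeks | None in the body text; general maximum 25 mg BID |
| Synopsis | Barred, no time limit | Barred for a recent hold | 25 mg BID |
| 6.2.1.2.1 | Barred for 28 days, toxicity at current dose level | Same | 25 mg BID |
| 6.2.1.2.2 | Barred, no time limit | Barred if platelets were under 50,000/µL or ANC under 1000/µL at any assessment | 25 mg BID |

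The synopsis list has no spleen or inadequate-response condition, and its step and minimum interval match those of 6.2.3.2. It is not worded as limited to efficacy increases.

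**Case A: reduction without a hold.** Platelets fall to between 25,000 and 50,000/µL on 5 mg BID. Table 6-3 removes 5 mg o.d.: 10 − 5 = 5 mg/day. The count then recovers to 50,000/µL.

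- 6.2.3.2: an increase is allowed, because its opening sentence covers increases as well as restarts.
- Synopsis: no increase, because there has been a safety-related reduction.
- 6.2.1.2.2: no increase, for the same reason and because the platelet history fails.

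**Case B: hold at platelets ≤25,000/µL or ANC <500/µL.** The patient restarts at 5 mg/day, half the starting 10 mg/day.

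- 6.2.3.2: steps are allowed every two weeks.
- 6.2.1.2.2: the every-assessment platelet or ANC condition fails for good, however the hold is classified.
- Synopsis: the interruption condition is time-limited. The no-reduction condition also applies if restarting lower counts as a reduction. The SAP (3.2) counts a hold followed by a lower dose as both, but that is an analysis convention and not a dosing rule.

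**Steps that the literal text of 6.2.3.2 permits.** Dose after k steps = 5 + 5k mg/day, at 2k weeks.

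- k = 1: 10 mg/day (5 mg BID, the starting dose) at 2 weeks.
- k = 9: 50 mg/day (25 mg BID, the general maximum) at 18 weeks.
- 50 / 10 = 5 times the starting daily dose.

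**Comparison with 6.2.3.1.** There the limit is the offending dose less 5 mg BID: a hold at 15, 20 or 25 mg BID leaves at most 10, 15 or 20 mg BID. Section 6.2.3.2 has no counterpart.

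**The case against.** The strongest reply is that these are two pathways. Section 6.2.1.2 deals with inadequate response: it asks for inadequate efficacy or a spleen increase of at least 2 cm. Section 6.2.3 deals with restarting and reinstating a previous dose. The 15–20 mg cohort has the same split, since 6.2.1.1.2 bars increases after a safety reduction while 6.2.3.1 allows re-escalation. On this reading, reinstatement ends at the previous dose, and a patient who was held for counts could not go beyond it because 6.2.1.2.2 would not be met. This is reasonable and may be what was intended. It rests on headings, however, and it does not explain the synopsis, whose conditions are general.

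A reader might infer four stronger points that the documents do not support:

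- *That increases carry no platelet threshold.* The opening sentence of 6.2.3.2 sets 50,000/µL for increases as well as restarts, and Table 6-3 requires a reduction or hold below that.
- *That the lowest-platelet group has the looser regime overall.* Its restart dose is 5 mg/day, against 10 mg/day (5 mg BID) in the lowest restart band of Table 6-4. Its steps are 5 mg/day, against up to 10 mg/day. It is looser only in lacking an explicit limit. Nor does the 6.2.3.1 formula transfer: its 100,000/µL trigger lies above this group's baseline counts, and 5 mg BID less than 5 mg BID is zero.
- *That any interruption bars increases permanently.* The interruption conditions in the synopsis and 6.2.1.2.1 are time-limited.
- *That patients would be taken to five times their starting dose.* This needs nine consecutive steps, each conditional on counts and adverse events. Sponsor approval is required before restarting after an adverse experience (6.2.6), and reduction, hold and discontinuation rules continue to apply.

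**Conclusion.** The point stands in limited form. For a 5 mg BID starter after a safety reduction, the synopsis and 6.2.3.2 give opposite answers as worded. After a haematologic hold, 6.2.1.2.2 and 6.2.3.2 do so unless they are separate pathways, which no passage states. The body of 6.2.3.2 neither ends reinstatement at the previous dose nor ties a limit to the dose that led to the hold, whereas 6.2.3.1 does state limits.

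The 18-week, five-fold figure is the outer edge of the literal wording and not an expected course. The documents do not say how many of the 2238 enrolled patients started at 5 mg BID or were later held or reduced, so the effect on exposure or cytopenia rates cannot be sized. The conclusion rests on the current synopsis and body text, not on the amendment log. It is worth correcting because it concerns dosing after a cytopenia in the group singled out for a safety interim.

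**What to change.** Reconcile the synopsis, 6.2.1.2.1, 6.2.1.2.2 and 6.2.3.2, with 6.2.3.1 alongside for comparison. State:

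1. which rule governs after a safety hold or reduction in a 5 mg BID starter;
2. where reinstatement under 6.2.3.2 ends and an increase under 6.2.1.2 begins;
3. whether the no-prior-safety-reduction condition applies beyond that point.

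The limits themselves are for the sponsor's medical team. The cost is protocol wording or an investigator letter. Closed enrolment does not remove the need, because the protocol lets treatment run to as late as 24 months after the last patient's first visit.
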